### 3.b.6. Participant Timeline.

After providing informed consent, and if the participant is determined to be eligible for continued participation, the appointment structure in each study phase is described below:

In the Open Trial Phase, if a participant is determined to be eligible following the baseline assessment, s/he will be assigned a CARE interventionist. Eligible participants will receive 3 individual sessions in prison in the time between the baseline assessment and the anticipated date of release from prison. A family/SO session (as applicable) will take place either in prison prior to release or as soon as possible after release either by telephone or in person (e.g., at our offices or in any residential facility where the participant is located, with facility approval). Ideally, the first two sessions will be delivered within 1 week, the third session will be delivered within the following week, and the family/SO session will be delivered within the week after that. However, we acknowledge that time to release will be variable, and the session schedule may be compressed or spread out depending upon length of time available to complete the sessions between the baseline assessment and the prison release date.

Following prison release, the counselor will initiate the phone follow-up calls, delivered across the first 6 months post-release. The schedule for phone follow-up will be: weekly for the first month, biweekly for the next 2 months, and then monthly for the final 3 months. Calls will be made separately to the prisoner participant and to the identified SO (if applicable).

In addition to the baseline assessment in prison, outcome assessments will occur on the following schedule: a) following the in-prison sessions, prior to prison release (~1-2 weeks prior to prison release); b) 1 month after prison release; and c) 6 months after prison release, immediately post-treatment. To enhance feasibility and therefore retention, we will aim to complete all post-release follow-up assessments by telephone, using procedures we have in place for other studies (see "Human Subjects Protections"). However, there may be some circumstances that might make it difficult for a participant to complete the follow-up assessment by telephone (e.g., rearrest and reincarceration, participation in a residential treatment program). In such cases, we will complete the follow-up assessment in person.

In the Pilot Randomized Trial Phase, if a participant is determined to be eligible following the baseline assessment, s/he will be randomized to either E-TAU plus CARE or to E-TAU alone.

**Randomization** will be determined in a 1:1 ratio, with 2 stratification variables, the maximum number advisable in a sample of this size: sex (male vs. female) and polarity of most recent mood episode (depression vs. (hypo)mania) using a randomization table.

Participants randomized to receive CARE will receive 4 counseling sessions. The first 3 sessions will be individual sessions that take place in prison in the time between the baseline assessment and the anticipated date of release from prison; or they will take place after release for those enrolled post-release. A fourth session will either be an individual counseling session or a family/SO session (as applicable). This session will take place either in prison prior to release or as soon as possible after release either by telephone, by zoom, or in person (e.g., at our offices or in any residential facility where the participant is located, with facility approval). Ideally, the first two sessions will be delivered within 1 week, the third session will be delivered within the following week, and the fourth session will be delivered within the week after that as either an individual session or a family/SO session. However, we acknowledge that time to release will be variable, and the session schedule may be compressed or spread out depending upon length of time available to complete the sessions between the baseline assessment and the prison release date. Following prison release (in prison enrollment) or completion of the initial sessions (post-release enrollment), the counselor will initiate the phone follow-up calls, delivered across the first 6 months post-release (in prison enrollment) or 6 months post-baseline (post-release enrollment). The schedule for phone follow-up will be: weekly for the first month, biweekly for the next 2 months, and then monthly for the final 3 months. Calls will be made separately to the prisoner participant and to the identified SO (if applicable).

Assessments will occur on the following schedule: For participants recruited in person at [REDACTED] prior to release: a) baseline assessment; b) following the in-prison sessions, prior to prison release (~1-2 weeks prior to prison release); c) 1 month after prison release; and d) 6 months after prison release, immediately post-treatment. For participants recruited post-release: a) baseline assessment; b) 1 month after baseline; and c) 6 months after baseline, immediately post-treatment. The post-release enrollment baseline would include any additional questionnaires/items from the pre-release assessment that were not already included in the baseline assessment. To enhance feasibility and retention, we will aim to complete all post-release follow-up assessments by telephone or zoom, using procedures we have in place for other studies (see "Human Subjects Protections"). However, there may be some circumstances that might make it difficult for a participant to complete the follow-up assessment by telephone or zoom (e.g., limited phone minutes, participant rearrest and reincarceration, current enrollment in a residential treatment program). In such cases, we will complete the follow-up assessment in person in our offices at [REDACTED] or in the facilities where the participant may be located (e.g., jail or prison, residential treatment facility). Additionally, if a participant is released earlier than expected before finishing the in-prison assessment, we will complete the assessment by

telephone, by zoom, or in person at our offices or in the facility (e.g., residential treatment program) where the participant is located.

Appointments for participants randomized to the E-TAU condition will consist of the regularly scheduled research assessments. For participants recruited in person at [REDACTED] prior to release: baseline, pre-release, 1 month post-release, and 6 months post-release. For participants recruited post-release: baseline, 1 month after baseline; and 6 months after baseline. The post-release enrollment baseline would include any additional questionnaires/items from the pre-release assessment that were not already included in the baseline assessment.

### **3.b.7. Audio recording.**

We will audio record all assessment interviews in order to perform reliability checks. Participants may refuse audio recording of assessments but still participate in the study. We will audio record all intervention sessions in order to monitor therapist adherence to the CARE manual. Participants may refuse audio recording of sessions and still participate in this study. With [REDACTED] permission to bring them into the prison facilities, we will utilize small, credit-card sized audio recorders that are password-protected and encrypted for purposes of safe transportation between the [REDACTED] facilities and [REDACTED] offices.

### **3.b.8. Assessment procedures.**

Participants enrolled prior to release will be assessed at: intake, just prior to prison release (4-10 weeks later, depending upon timing of baseline and scheduled release date), and then at 1 and 6 months post-release. Participants enrolled post-release will be assessed at: intake, and then at 1 and 6 months post-release. The post-release enrollment baseline will consist of any items in the pre-release that were not included in the baseline. In addition to demographics, we will assess psychiatric diagnosis (primary inclusion criterion), psychiatric symptom severity, substance use history, psychosocial functioning, proposed mechanisms of action for the intervention (i.e., values-action consistency, social support, mental health and substance use treatment utilization and adherence), and treatment satisfaction. Assessments are listed in Table 2. RAs will also call to verify/update locator information monthly after release.

All interview and self-report assessment measures were chosen because they have strong psychometric properties for measurement of the constructs of interest to the study, and have been used in other NIH-funded clinical trials and prospective studies. With signed releases of information (ROIs) obtained at the baseline assessment, we will supplement interview and self-report data with criminal justice and medical records chart review to assess for recidivism and community treatment utilization, respectively.

Table 2: Pre-Release Enrollment Schedule of Assessments	Type	Baseline	Pre-release, 1mo & 6mo post- release
Diagnosis: Structured Clinical Interview for DSM-5 	Interview	X	
Psychiatric Symptom Severity			
LIFE – PSRs for depression and mania 	Interview	X	X
Quick Inventory of Depressive Symptomatology 	Self-report	X	X
Altman Self-Rating Scale for Mania 	Self-report	X	X
LIFE – suicidal ideation and behavior 	Interview	X	X
Substance Use			
Alcohol Use Disorders Identification Test 	Self-report	X	1 & 6 mo only
Drug Use Disorders Identification Test 	Self-report	X	1 & 6 mo only
Psychosocial Functioning			
SF-12 from RAND Medical Outcomes Study 	Self-report	X	X

Job Security Index/Job Satisfaction Scale 	Self-report		1 & 6 mo only
Housing Security Scale 	Self-report		1 & 6 mo only
Criminal Justice Records Review	Objective		X
Targeted Mechanisms of Action			
Valued Living Questionnaire 	Self-report	X	X
Multidimensional Scale of Perceived Social Support 	Self-report	X	X
NIH Toolbox Instrumental Support Fixed Form Age 18+ v2.0 	Self-report	X	X
Treatment History Interview-4 	Interview	X	X
Brief Adherence Rating Scale 	Interview	X	X
Medical Records Review	Objective	X	X
Participant Satisfaction			
Client Satisfaction Questionnaire-8 	Self-report		6 mo only
End of Intervention Questionnaire	Self-report		6 mo only
Exit Interview	Interview		6 mo only
COVID-19			
Coronavirus Impact Scale			6 mo only

**Please note:** The post-release enrollment assessments are the same as the pre-release enrollment assessments. However, the schedule of assessments is slightly different. Post-release enrolled participants will not complete a pre-release assessment. Items specific to the pre-release assessment that are not already included in the baseline assessment are added to the baseline for post-release enrolled participants.

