- 3) Conduct a randomized pilot trial in 40 prisoners with BD, comparing CARE to TAU to demonstrate the *feasibility* and *acceptability* of the proposed recruitment methods, research design, intervention, and counselor training program, with assessment at baseline, pre-release, and 1 and 6 months post-release. For those recruited post-release, assessments will be at baseline, 1 month and 6 months.
- 4) Examine 95% confidence intervals around differences between CARE and TAU for the following outcomes: reduced mood symptoms (*primary*); suicidal ideation and behaviors, substance use, rates of re-arrest, and more stable employment and housing (*secondary*);
- 5) Examine 95% confidence intervals around differences between CARE and TAU to evaluate differential engagement of purported mechanisms of action: increased values-action consistency, practical and emotional social support, and increased treatment engagement (i.e., utilization and adherence).

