Community treatment Adherence at Re-Entry (CARE) intervention. CARE will begin within the 2 months preceding prison release, and will continue for 6 months following community re-entry. Or, for those enrolled post-release, CARE will begin right after enrollment and continue for 6 months. CARE will be comprised of: a) 3 individual sessions with the CARE counselor prior to prison release or right after prison release; b) either a fourth individual session or 1 family/significant other (SO) session either prior to prison release or as soon as possible after release into the community (when applicable); and c) a series of 11 brief (15-20 min) follow-up telephone contacts with prisoners and their SO. If a participant is released earlier than expected before finishing the in-prison sessions or if the participant is recruited after release from prison, we will complete the sessions by telephone, by zoom, or in person at our offices (or in any residential facility where the participant is located, with facility approval).

The CARE intervention will incorporate motivational strategies from existing interventions in order to clarify values and goals to enhance motivation for behavior change. These strategies will be primarily derived from Acceptance and Commitment Therapy (ACT; note that this is different from Assertive Community Treatment), a “third wave” cognitive-behavioral approach that has demonstrated efficacy in a wide range of disorders, including mood disorders, psychosis, and SUDs. ACT proposes that a discussion and clarification of the patient’s personal values can facilitate motivation, hopefulness about the future, and behavior change. Values are defined as broad, personally defined verbal constructs that provide the context for more specific behaviorally consistent goals. Values provide a personal rationale that can help motivate individuals to remain committed to desired actions, even if they are associated with other undesirable consequences. In contrast, goals represent more narrowly defined desired consequences that can be impeded by various internal and external factors. Procedures have been developed to clarify values and goals in order to assess and decrease discrepancies (thereby promoting consistency) between patient values and daily actions. Such values strategies will inform the initial, sessions with the patient and SO, and culminate in an individualized “Re-entry Plan”

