### **3.b.10. Material inducements.**

We will compensate participants \$40 for each of the three follow-up assessments for pre-release enrolled participants (immediate pre-release, 1 month post-release, 6 months post-release) in the form of a money order or a gift card (if they do not have state or federal identification to cash the money order). For post-release enrolled participants, they will be compensated \$40 for each of their completed assessments (baseline, 1 month follow-up, and 6 month follow-up). In total, participants may receive up to \$120 if they complete all study assessments. Compensation for the pre-release assessment will be mailed to an address of the participant's choosing after it is confirmed that the participant has been released from prison. If a follow-up is completed in jail or prison, we will provide the participant the following options: a) us mailing the compensation once they are released, or b) mailing it to a family member or significant other of their choosing, or c) depositing it into their commissary account at the [REDACTED]

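### For participants enrolled after release, Section 3.b.8 dates the 1- and 6-month visits from release, but Section 3.b.6 dates them from baseline; followed literally, 3.b.8 puts the final visit before CARE ends

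*Combined protocol and SAP*

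**What the plan says.** The visit schedule of participants enrolled after release is stated five times.

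- **Section 3.b.6 (Participant Timeline), general schedule:** baseline, 1 month after baseline, and a last visit at "6 months after baseline, immediately post-treatment".
- **Section 3.b.6, E-TAU appointments:** "For participants recruited post-release: baseline, 1 month after baseline; and 6 months after baseline".
- **Section 3.b.8 (Assessment procedures):** "Participants enrolled post-release will be assessed at: intake, and then at 1 and 6 months post-release".
- **Section 3a (Aims), pilot aim 3:** "For those recruited post-release, assessments will be at baseline, 1 month and 6 months", with no starting point for the months.
- **Section 3.b.10 (Material inducements):** payment for "completed assessments (baseline, 1 month follow-up, and 6 month follow-up"), again with no starting point.

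Table 2 in 3.b.8 is titled for pre-release enrollment. Its note says the schedule for the other route differs slightly, but the only differences it names are that "Post-release enrolled participants will not complete a pre-release assessment" and that the items specific to that visit move to baseline.

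On treatment timing, Section 3.b.2 says that for this route "CARE will begin right after enrollment and continue for 6 months". Section 3.b.6 likewise runs the telephone calls to 6 months after baseline for these participants. Section 3.b.1 admits people with a recent release and sets no upper limit on how recent.

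**The concern.** Two current sections give different dates for the same visits, and nothing says which governs. Someone working from 3.b.8, the section on assessments, never meets the baseline rule. The sentence just before the conflicting one uses the same term for time since release, so nothing in the text suggests reading it differently here.

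Two things depend on the date of the 6-month visit.

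- **Acceptability.** Table 2 gives the CSQ-8, the "End of Intervention Questionnaire" and the Exit Interview at 6 months only. Section 3.b.9 uses them to judge acceptability, which is part of the pilot's primary goal. They are meant to follow the intervention, not to be given while it is still running.
- **Mood symptoms.** Section 2 places the primary outcome in a 6-month follow-up window, and this visit closes it. If some staff follow 3.b.6 and others 3.b.8, visit timing will vary within one enrollment route, in a group-by-time model with 40 participants.

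**Working it through.** The plan gives no figure to reproduce; the check is timeline arithmetic.

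**Inputs**

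- Visits at 1 and 6 months after release (3.b.8), or at 1 and 6 months after baseline (3.b.6).
- CARE ends 6 months after enrollment or baseline (3.b.2, 3.b.6).
- g = weeks from release to baseline. The documents do not state it; 2, 4 and 8 weeks are **assumed** for illustration.
- 1 month = 365.25/12 = 30.44 days = 4.348 weeks, so 6 months = 26.09 weeks.

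**Formulas, in weeks after baseline**

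- 3.b.6: visits at 4.348 and 26.09, whatever the value of g.
- 3.b.8: visits at 4.348 − g and 26.09 − g.
- CARE still to run at the final visit under 3.b.8: 26.09 − (26.09 − g) = g.
- Fraction by which the time to the final visit is shortened: g/26.09.

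| g (assumed) | 1-month visit, 3.b.8 | Final visit, 3.b.8 | CARE still to run | Shortening to final visit |
|---|---|---|---|---|
| 0 weeks | 30.4 days after baseline | 26.09 weeks | 0 weeks | 0% |
| 2 weeks | 2.35 weeks = 16.4 days after | 24.09 weeks | 2 weeks | 2/26.09 = 7.7% |
| 4 weeks | 0.35 weeks = 2.4 days after | 22.09 weeks | 4 weeks | 4/26.09 = 15.3% |
| 8 weeks | −3.65 weeks = 25.6 days **before** | 18.09 weeks | 8 weeks | 8/26.09 = 30.7% |

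The g = 0 row is also the 3.b.6 schedule, so the two sections agree only for someone assessed on the day of release.

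**Where the shift falls.** The interval from the 1-month to the 6-month visit is 26.09 − 4.348 = 21.74 weeks under both rules. The whole shift is therefore taken from the interval between baseline and the 1-month visit: 2/4.348 = 46% of it at 2 weeks and 4/4.348 = 92% at 4 weeks. The 1-month visit is due before intake when 4.348 − g < 0, that is, when g exceeds 4.35 weeks (30.4 days).

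**Calls outstanding.** The call schedule in 3.b.6 gives 4 weekly + 4 biweekly + 3 monthly = 11 calls. Spacing them from baseline at weeks 1–4, 6, 8, 10 and 12 and months 4, 5 and 6, the calls still due at the 3.b.8 final visit number 1, 1 and 2 for gaps of 2, 4 and 8 weeks.

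**Which rule is the wrong one.** Of the five statements, two date from baseline (both in 3.b.6), one from release (3.b.8) and two give no starting point (3a, 3.b.10). The treatment period in 3.b.2 and 3.b.6 also runs from enrollment or baseline. Only the baseline rule makes the last visit coincide with the end of CARE.

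**The case against.** The best reply is that the intended schedule is clear. Section 3.b.6 is the dedicated timeline, sets this route out separately and repeats it for E-TAU, and the treatment period agrees with it. The sentence in 3.b.8 only introduces the instrument list and is probably left over from the pre-release wording. With a long gap it defeats itself, because nobody can hold a 1-month visit before intake, so staff would turn to 3.b.6. With a short gap the shift is small. The gap and the number of post-release enrollees are both unstated. The CARE time cut off contains only about one or two calls of 15–20 minutes, and the completion rule in 3.b.9 (at least 3 of 4 initial sessions and 6 of 11 calls) could already be met. Sections 3.c.4 and 3.c.6 also speak of 1 and 6 months post-release, which suggests a general carry-over.

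Much of this stands. The wording is probably a leftover, the size of the shift rests on assumed gaps, and no effect on satisfaction answers has been shown. Section 3.b.9 does not define the follow-up window for the primary outcome; the 6-month window comes from Section 2. None of it removes the conflict. The sentence in 3.b.8 was written for this route and names a definite starting point. At gaps under about 4.3 weeks it can be carried out, and it gives the wrong date. Sections 3.c.4 and 3.c.6 describe the in-prison route, so they are not further contradictions, but they make the release date easier to apply by mistake.

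**Conclusion.** The concern holds. Section 3.b.8 contradicts 3.b.6 for participants enrolled after release, and the protocol itself shows that 3.b.8 is the one to correct. Taken literally, it puts the final visit before the end of CARE by exactly the release-to-baseline gap, for any gap above zero. At assumed gaps of 2 to 8 weeks, that is 8% to 31% of the 6 months. Above about 4.35 weeks the 1-month visit cannot be held as scheduled.

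The existence of the conflict does not depend on the assumed gaps; its size does. It also depends on how many of the 40 participants enter after release, which the documents do not state. Both arms share the visit dates, so the comparison of CARE with E-TAU is not biased by this. The cost would be acceptability data collected before treatment ends and uneven visit timing if staff follow different sections. The importance is low to moderate, and the correction should be made.

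The two routes also differ by design in time from baseline to the final visit: 4 to 10 weeks plus 26.09, or about 30 to 36 weeks, for pre-release enrollees, against about 26 weeks for the others. That is a separate matter, and this correction does not change it.

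**What to change.** In the 3.b.8 sentence on participants enrolled after release, keep the intake visit and date the two follow-up visits 1 and 6 months *after baseline* instead of after release. This matches both statements in 3.b.6 and the CARE period in 3.b.2 and 3.b.6, and it puts the visits at 1 and 6 months after baseline whatever the gap.

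The cost is one phrase in one sentence, with no added visits, participants, variables or analyses. In the same edit it would help, though it is not essential, to state the baseline dating in the note under Table 2.

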### **3.b.9. Data analysis.**

For this pilot effectiveness study, assessment of feasibility and acceptability of the intervention and research procedures is the primary goal. Nonetheless, pilot data can be used to demonstrate whether the effects of treatment look promising across a set of outcome variables, to begin to examine distribution of outcome variables to inform future analytic strategies, and to suggest, in concert with results from larger scale clinical trials in related fields, the range of effect sizes that would be reasonable to expect in a future trial.

Study Feasibility and Treatment Feasibility/Acceptability. One of the primary goals of a pilot study is to demonstrate the feasibility of the proposed treatment and of the study and recruitment methods. As a result, we will assess the feasibility of the research procedures by examining study recruitment and refusal rates, participants' willingness to be randomized, follow-up rates, reliability and range of responses to study questionnaires, and success of the interventionist training program. We will assess the feasibility and acceptability of CARE by examining rates of treatment attendance, rates of treatment completion (attending at least 3 of the 4 initial sessions and completing 6 out of the 11 scheduled post-release telephone calls) and drop-out, and reports on the End of Intervention Questionnaire. We will also examine reasons for termination for consistent patterns. We will examine the acceptability of both CARE and E-TAU using data from CSQ-8 treatment satisfaction and end of intervention questionnaires and detailed exit interviews.

Primary Outcomes: Using multilevel modeling of group by time, we will calculate the effect size and 95% CI for percent time symptomatic using the LIFE, with percent time symptomatic in the 90 days prior to study enrollment as a covariate. We will calculate similar exploratory tests for symptom severity using the QIDS and ASRM total scores, with baseline scores as covariates.

Secondary Outcomes: Using multilevel modeling of group by time, we will calculate the effect sizes and 95% CIs for: (1) percent time suicidal, as assessed by the LIFE, (2) alcohol and drug use severity using the AUDIT and DUDIT, respectively, and (3) overall functioning, employment stability, and housing stability, using the SF-12, JSI, and HSS, respectively. All assessments will use baseline scores, including percent time suicidal in the 90 days prior to study enrollment, as covariates. Potential group differences in rate of re-arrest will be calculated using simple chi-square analysis.

Target engagement/mechanisms of action. In this study, we will explore potential group differences in CARE's purported mechanisms of action. To that end, we will rely upon multilevel modeling of group

by time to calculate effect sizes and 95% CIs for change in VLQ, NIH Toolbox Instrumental Support, MSPSS, THI, and BARS scores across study time points. Across the four assessment time points, we will also evaluate associations between change in these intermediary constructs and primary/secondary outcome measures, using multilevel models.

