**3a. Aims:**

The primary aim of this pilot effectiveness trial is to develop and establish the feasibility, acceptability, and potential for future uptake of CARE (Community treatment Adherence at Re-Entry), an innovative, moderate intensity intervention that combines evidence-based cognitive-behavioral, family, and telephone outreach strategies to promote community treatment engagement and thereby improve clinical outcomes for prisoners with bipolar disorder (BD) across the period of community re-

entry. Development of CARE will be informed by our experiences successfully piloting a similar intervention (the Integrated Treatment Adherence Program; ITAP) for individuals with BD and comorbid substance dependence across another vulnerable transition, from inpatient to outpatient care in the community. As an adaptation of ITAP for community re-entry, CARE will be designed to be delivered by a range of clinicians, providing advantages for scalability in the resource-poor criminal justice system. Its proposed mechanisms of action (i.e., increasing values-action consistency, enhancing social supports, and linkage to community treatment services, all to promote treatment engagement, thereby improving clinical outcomes) are further well-matched to the practical and clinical needs of re-entering individuals.

The secondary aim of this research will be to compare outcomes, within 95% confidence intervals, between CARE as an adjunct to treatment as usual (TAU) vs a TAU control condition. In keeping with ethical obligations, we will enhance TAU by providing post-release monitoring and emergency referral, as needed. We will explore future dissemination potential by using community mental health counselors for treatment delivery.

The *development* aims of this project are to:

- 1) Develop a comprehensive treatment manual, interventionist training program, and fidelity scales for CARE, comprised of 3-4 individual sessions prior to release, and 1 family meeting (when applicable), followed by a series of 11 brief telephone outreach contacts up to 6 months post-release.
- 2) Improve the clarity, content, acceptability, and feasibility of CARE through a small open trial (n=12) of prisoners with BD treated through 6 months post-release, followed by stakeholder interviews (participants, prison staff, community mental health partners) as part of the refinement process.

The *pilot study* aims of this project are to:

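### Pilot aim 4 promises a 95% CI for the CARE–TAU difference in re-arrest, but the analysis section plans only a chi-square test for it

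*Combined protocol and SAP*

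**What the plan says.** Section 3a sets interval estimation as the way the arms are to be compared. The secondary aim is to "compare outcomes, within 95% confidence intervals, between CARE as an adjunct to treatment as usual (TAU) vs a TAU control condition". Pilot aim 4 repeats this: "Examine 95% confidence intervals around differences between CARE and TAU for the following outcomes". Its list of secondary outcomes reads "suicidal ideation and behaviors, substance use, rates of re-arrest, and more stable employment and housing", so re-arrest is plainly covered.

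Section 3.b.9, under Secondary Outcomes, keeps that promise for most of the list. By multilevel modelling, "we will calculate the effect sizes and 95% CIs for: (1) percent time suicidal", followed by alcohol and drug use severity, overall functioning, employment stability and housing stability. Re-arrest is then handled in a separate sentence: "Potential group differences in rate of re-arrest will be calculated using simple chi-square analysis". No other section plans an analysis of re-arrest.

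**The concern.** The aim and the analysis do not match. A chi-square test measures evidence against equal proportions. It does not say how large the difference is or which differences remain compatible with the data. The interval cannot be taken as implied, because the same paragraph names intervals for the other outcomes and omits them here.

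What is at stake is what the pilot can hand to the larger trial. The opening of section 3.b.9 says pilot data should help suggest a plausible range of effect sizes for a future trial. A p-value alone gives no such range.

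**Working it through.** **Inputs.** Section 3a: "Conduct a randomized pilot trial in 40 prisoners with BD". Section 3.b.1 gives 20 in the CARE arm, and section 3.b.6 gives 1:1 allocation, so n = 20 per arm. The documents state no re-arrest rate, power or effect size, so there is no figure of the plan's own to reproduce. All counts below are assumptions for illustration.

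**Formulas.** Pearson chi-square without continuity correction: the sum of (observed − expected)²/expected over the four cells. Newcombe 95% CI for d = p1 − p2, with Wilson limits (l1, u1) and (l2, u2) for each arm:
- lower = d − √[(p1 − l1)² + (u2 − p2)²]
- upper = d + √[(u1 − p1)² + (p2 − l2)²]

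The Wilson limits are [p + z²/2n ± z√(p(1−p)/n + z²/4n²)] / (1 + z²/n), with z = 1.96.

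**Example 1: CARE 4/20, E-TAU 8/20.**
- Expected counts per arm: 12/2 = 6 re-arrested and 28/2 = 14 not.
- Chi-square = 2 × (4/6) + 2 × (4/14) = 1.90, p = 0.17 (0.30 with continuity correction).
- Wilson limits: 0.081 to 0.416 for 4/20, and 0.219 to 0.613 for 8/20.
- d = 0.20 − 0.40 = −0.20.
- Lower = −0.20 − √(0.0142 + 0.0455) = −0.444. Upper = −0.20 + √(0.0467 + 0.0328) = +0.082.
- Result: −20 points, 95% CI −44 to +8.

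**Example 2: 5/20 in each arm.**
- Chi-square = 0, p = 1.00.
- Wilson limits: 0.112 to 0.469 in each arm.
- Half-width = √(0.0191 + 0.0478) = 0.259.
- Result: 0 points, 95% CI −26 to +26.

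Example 2 is the more telling. The p-value could not be larger, yet the counts remain compatible with a 26-point difference in either direction. Only the interval shows this, and the interval is what aim 4 asks for.

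**Is the chi-square itself unsound at this size?** This was checked by enumerating all 21 × 21 possible tables at 20 per arm, with the same true rate in both arms (uncorrected test, nominal 5%):

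| True re-arrest rate | True size of test |
|---|---|
| 5% | 1.2% |
| 10% | 3.9% |
| 15% | 4.9% |
| 20% | 5.0% |
| 30% | 5.3% |

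At a 20% rate an expected count falls below 5 in 73% of trials, and at 15% in 93%. Even so, the size stays close to nominal at both rates. Of the rates checked, the test is clearly off only at 10% and 5%, and there it is conservative.

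**The case against.** The strongest reply is that little is lost. Re-arrest is one secondary outcome in a pilot whose primary goal is feasibility and acceptability, no decision rule hangs on the test, and anyone holding the 2×2 table can compute the interval later. That stands as an argument about severity. It does not remove the mismatch, because the stated aim is the interval and the plan does not produce it.

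A reader might infer three stronger criticisms. The documents do not support them.

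- **The test is too weak to use.** Imprecision comes from having 40 participants, and the Newcombe intervals above are wide for the same reason. The documents claim no efficacy power, so low power is not a fault of choosing chi-square.
- **The large-sample approximation fails.** The enumeration shows size near 5% at rates of 15% to 30%. The point is limited to rates of about 10% or less, where the error is conservative.
- **Ignoring time at risk makes the analysis invalid.** The proportion re-arrested over a 6-month window is a legitimate target, randomisation balances exposure in expectation, and records review can capture arrests after contact is lost. Aim 4 does not ask for time to event. A rate per person-month at liberty would need arrest and custody dates, and sections 3.b.8 and Table 2 do not say these will be abstracted.

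One thing remains from the timing argument. The re-arrest window is not defined. For people enrolled after release, section 3.b.6 counts 6 months from baseline, while the opening of section 3.b.8 counts from release. Any statement of the proportion needs one origin.

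**Conclusion.** The gap is real and narrow. Section 3a commits to a 95% CI for the between-arm difference in re-arrest, section 3.b.9 plans only a p-value, and nothing elsewhere supplies the interval. At 20 per arm the omission matters for interpretation: in the assumed examples p-values of 0.17 and 1.00 sit beside intervals about 53 points (−44 to +8, before rounding −44.4 to +8.2) and 52 points (−26 to +26) wide. Those widths rest on the assumed counts, on full ascertainment of all 40 participants and on the Newcombe method. The mismatch itself rests on no assumption. It should be corrected, but it threatens neither the pilot's primary feasibility goal nor its primary outcome.

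**What to change.** Replace or supplement the re-arrest sentence in section 3.b.9 with: *The proportion re-arrested within the 6-month follow-up will be compared as the CARE minus E-TAU risk difference with a 95% Newcombe or Miettinen-Nurminen CI.* The chi-square p-value may stay as a supplement. State the origin of the 6 months for each enrolment route once sections 3.b.6 and 3.b.8 have been reconciled.

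The cost is a sentence or two of wording. The interval uses the same 2×2 counts as the chi-square, so it needs no new data. A display of time to first re-arrest is optional, and only if the criminal justice records reviewed carry arrest dates.
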